1.4. Rationale for Dose Selection of Lenacapavir

The dose selection for LEN in this study is supported by antiviral activity, PK, and safety data from the completed Phase 1b proof-of-concept (POC) Study (GS-US-200-4072) in treatment-naïve (TN) and TE but capsid inhibitor (CAI)–naïve PWH, as well as PK and safety data from the 2 Phase 1 studies in healthy volunteers (Study GS-US-200-4538 and Study GS-US-200-4071).

In the completed Phase 1b POC study (GS-US-200-4072), potent antiviral activity of LEN has been demonstrated; the mean maximum HIV-1 RNA decline over 10-day monotherapy after single SC doses of 50 to 450 mg was 1.8 to 2.2 log₁₀ copies/mL. All participants achieved at least 1 log₁₀ copies/mL decline in their HIV-1 RNA at Day 10. Day 10 antiviral activity was comparable across a dose range of single doses of 50 to 450 mg. At these doses, mean (%CV) LEN concentrations on Day 10 were 1.1- to 9.9-fold higher (eg, IQ: 1.1-9.9) than the paEC₉₅ for wild-type HIV-1 (paEC₉₅ = 3.87 ng/mL in MT-4 cells) (see the current edition of the IB).

Phenotypic analyses of LEN susceptibility in patient derived isolates indicate that isolates from TN and HTE PWH have a similar in vitro profile, suggesting similar LEN antiviral activity should be observed in the HTE patient population compared to the TN patient population.

Based on these data, a concentration of 15.5 ng/mL (corresponding to an IQ of 4 based on paEC₉₅ from MT-4 cells), is anticipated to provide antiviral activity in the HTE population.

Lenacapavir formulations and doses to be evaluated in this study are informed by PK and safety data from Phase 1 Studies GS-US-200-4071 and GS-US-200-4538 in healthy volunteers. The proposed regimen targets an exposure whereby the lower bound of the 90% CI of the C_{trough} is 4-fold higher than the paEC₉₅ (ie, IQ4) within a few days of dosing initiation, at Day 14 (end of Functional Monotherapy Period), and at end of the dosing interval (once every 26 weeks).

As described in the IB, the LEN SC solution formulation exhibits a slow initial release necessitating an oral PK load regimen prior to the first SC injection (GS-US-200-4538 clinical study report [CSR]). In Study GS-US-200-4625, to achieve IQ4 within a few days of dosing and to maintain target concentrations through the Functional Monotherapy Period, participants will receive oral tablet doses of LEN 600 mg on Days 1 and 2 and an oral tablet dose of LEN 300 mg on Day 8.

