5.4. Dosing and Administration of Oral Weekly Bridging of Lenacapavir

Participants may require oral weekly bridging if an SC injection of LEN cannot be administered for any reason within the protocol visit window.

- If 26 to 28 weeks elapses since the last SC injection and if clinically appropriate to continue LEN, start oral LEN 300 mg (1 tablet) once a week at Oral Bridging visit(s) and continue weekly dosing on the same day of the week.
- If more than 28 weeks elapse since the last SC injection and if clinically appropriate to continue LEN, restart the oral lead-in at the Oral Bridging visits and continue oral weekly dosing on the same day of the week, until SC LEN is administered ([Table 2](#)).

Table 2. Dosing Schedule for Oral Weekly Bridging and Resumption of SC Lenacapavir Injection

26 to 28 weeks of elapse since the last SC injection	More than 28 weeks of elapse since the last SC injection	LEN Dose
Treatment time from oral start	Dose	—
NA	Day 1 ^a	Oral 600 mg (2 × 300 mg tablets)
NA	Day 2	Oral 600 mg (2 × 300 mg tablets)
Day 1 ^a	Day 8; continue oral weekly LEN on the same day of the week as first dose until LEN SC is administered	Oral 300 mg (1 × 300 mg tablet)
Day 8; continue oral weekly LEN on the same day of the week as first dose until LEN SC is administered	NA	Oral 300 mg (1 × 300 mg tablet) once a week
SC administration restart (within 1 week of the oral weekly 300 mg dose [as early as after Day 1 dosing])	SC administration restart (within 1 week of the oral weekly 300 mg dose [as early as after Day 8 dosing])	SC 927 mg every 6 months ^a

LEN = lenacapavir; NA = not applicable; SC = subcutaneous

^a Day 1 oral dosing and SC LEN will be administered on site, otherwise, all other oral dosing will be administered at home, but can be done on site at the investigator’s discretion.

- For oral weekly bridging, the administration of the first dose will occur on-site and up to 2 bottles of LEN will be given to the participant to take oral LEN at home; further on-site oral dosing may occur at investigator’s discretion. Up to 2 additional bottles may be given to the participant as needed upon completion of previously dispensed bottles.
- Participants may continue receiving oral weekly LEN 300 mg until they can receive their next SC LEN injection.

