- Cohort 2 participants will receive SC LEN 927 mg at the Day 1 SC visit while continuing on their OBR (14 days after the first dose of oral LEN). Participants will continue to receive SC LEN 927 mg every 6 months (26 weeks) \pm 2 weeks from last injection thereafter while continuing their OBR.
- SC study drug administration will occur at the study center without regard to food.
- Provide ISR assessment worksheet and instruct the participants to measure and report ISRs following the administration of the SC injections.
- For all participants on oral weekly bridging, the first dose of oral LEN will be administered at the study center without regard to food and up to 2 bottles will be provided to the participant with instructions to take the remaining doses at home once a week (1 \times 300 mg LEN) without regard to food on the same day of the week that the first dose was given.
- Document study drug administration.
- Document study drug accountability.
- Participants who meet the criteria for virologic failure will be managed according to the Management of Virologic Failure Section 6.7.

The Week 156 visit and visits every 26 weeks thereafter are to be completed within \pm 2 weeks of the protocol-specified visit date. Each SC LEN dosing should occur within 26 weeks \pm 2 weeks of the previous SC LEN dosing.

The following procedures are to be completed at all visits unless otherwise noted.

- Review of AEs and changes in concomitant medications.
- Symptom-directed physical examination.
- Obtain vital signs and body weight.
- Obtain blood and urine samples as noted in Section 6.5.
- SC study drug administration will occur at the study center without regard to food.

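### The home-dosing instruction for oral bridging in Protocol Section 6.3.2 has no place for the 600 mg Day 2 dose that Table 2 requires when bridging starts more than 28 weeks after the last injection

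*Protocol*

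**What the plan says.** Two places in the protocol tell sites how to dose a participant who bridges orally.

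**Section 5.4 and Table 2** distinguish two cases by time since the last SC injection. At 26 to 28 weeks, the participant takes 300 mg on Day 1 and 300 mg weekly after that. Beyond 28 weeks the rule is different: "If more than 28 weeks elapse since the last SC injection and if clinically appropriate to continue LEN, restart the oral lead-in". The later column of Table 2 then gives 600 mg on Day 1, 600 mg on Day 2, 300 mg on Day 8, and 300 mg weekly until the injection is given. Footnote a settles where doses are taken: "Day 1 oral dosing and SC LEN will be administered on site, otherwise, all other oral dosing will be administered at home", with on-site dosing allowed at the investigator's discretion. The table's title, "Dosing Schedule for Oral Weekly Bridging and Resumption of SC Lenacapavir Injection", applies to both columns.

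**Section 6.3.2** (Maintenance Period Assessments) contains a bullet with no split at 28 weeks. It begins "For all participants on oral weekly bridging, the first dose of oral LEN will be administered at the study center". It continues that "up to 2 bottles will be provided to the participant with instructions to take the remaining doses at home once a week", specifies one 300 mg tablet per dose, and ends "without regard to food on the same day of the week that the first dose was given".

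Section 5.4 has its own dispensing bullet, "up to 2 bottles of LEN will be given to the participant to take oral LEN at home". It states neither a dose nor a home schedule, so it fits both columns of Table 2.

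**The concern.** The Section 6.3.2 bullet reproduces the 26 to 28 week schedule but is addressed to all bridging participants. For a start after 28 weeks it conflicts with Table 2 on the Day 2 dose.

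The Day 2 dose has a stated purpose. Section 1.4 explains that the oral lead-in, including 600 mg on Days 1 and 2, is given "to achieve IQ4 within a few days of dosing and to maintain target concentrations through the Functional Monotherapy Period". Section 1.5 supports weekly 300 mg without a reload only when bridging starts 26 to 28 weeks after the last injection. Late starters have gone longest without an injection, and Section 1.6 names prolonged subtherapeutic exposure after dosing stops as a resistance risk.

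The location of the error matters too. Section 5.3 has the whole initial lead-in given on site, whereas the restarted lead-in's Day 2 dose is by default taken unsupervised at home. What the participant is told when the bottles are handed over is therefore an important safeguard for that dose, and this bullet is the text that says what to tell them. Table 3 covers missed weekly doses only and would not pick up an omitted Day 2 dose.

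**Working it through.** This is mainly a comparison of texts. The plan states no figure to reproduce.

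**Step 1. The two instructions side by side**

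| Start of bridging | Dose | Table 2 (Section 5.4) | Section 6.3.2 bullet |
|---|---|---|---|
| 26 to 28 weeks | Day 1 | 300 mg, on site | On site, amount not stated |
| | Day 2 | None | None |
| | Day 8 and weekly | 300 mg | 300 mg |
| After 28 weeks | Day 1 | 600 mg, on site | On site, amount not stated |
| | Day 2 | 600 mg, at home by default | No place for it |
| | Day 8 and weekly | 300 mg | 300 mg |

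The two agree for starts at 26 to 28 weeks. For later starts they differ on Day 2 only. Day 1 is not in conflict, because the bullet gives no first-dose amount.

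**Step 2. Is Day 2 excluded, or only unmentioned?** The bullet's weekly interval, one-tablet dose and weekday rule apply to all doses after the first. Counting from Day 1, those doses fall on Days 8, 15, 22 and so on. A two-tablet dose on Day 2 fails all three conditions, so it is excluded.

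**Step 3. Size, as a conditional illustration.** Assume Day 1 is given per Table 2 and the home doses are instructed from the bullet. No section prescribes that combination.

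- Table 2, after 28 weeks, through Day 8: 600 + 600 + 300 = 1500 mg, or 5 tablets of 300 mg.
- Table 2 Day 1 plus the bullet, through Day 8: 600 + 300 = 900 mg, or 3 tablets.
- Difference: 1500 − 900 = 600 mg, or 2 tablets. This is exactly the Day 2 dose, and 600 / 1500 = 40% of the total.

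**Step 4. Would supply prevent the correct dose?** Section 5.2.2 gives 4 or 5 tablets per bottle, so two bottles hold 2 × 4 = 8 to 2 × 5 = 10 tablets. The Day 2 dose uses 2. That leaves 6 to 8 tablets for weekly doses if Day 1 comes from other stock, or 4 to 6 if Day 1 also comes from these bottles; the documents do not say which. Supply is sufficient either way.

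**The case against.** The strongest reply is that the protocol already protects the affected group. A start after 28 weeks is outside the dosing window. Section 5.3 then calls for immediate sponsor contact, makes continuation subject to medical monitor approval, warns that extra oral doses may be needed, and points to Section 5.4. Sections 3.3 and 6.3.2 and footnote v of Appendix 2 also send bridging dosing to Section 5.4. A site that follows any of these will dose correctly. This stands, and it limits how often the error could matter. It does not make the bullet correct.

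A second reply is that the bullet covers only the weekly phase, after any restarted lead-in. Some text, such as Section 1.5, does use the term for weekly 300 mg alone, and Table 2's later column has a similar weekday clause alongside a Day 2 dose. However, the Section 5.4 heading and the Table 2 title use the term for both schedules. Table 2's weekday clause attaches to the weekly phase, while the bullet's attaches to every remaining dose. If the bullet's first dose meant Day 8 for late starters, that dose would have to be given on site, which contradicts footnote a. This reading does not resolve the conflict.

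Third, little exposure may remain. SAP Section 2.1.4 reports an oral bridging analysis conducted after all participants who had bridged had resumed injections or discontinued. The Amendment 5 history puts 13 participants on study, and the procedure list for Week 156 onward omits the bullet. All of this is fair. It does not rule out later bridging, which the current protocol still provides for.

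**Conclusion.** The inconsistency is real and confined to one dose. For bridging started more than 28 weeks after the last SC injection, the Section 6.3.2 home instruction leaves no place for the 600 mg Day 2 dose that Table 2 requires. It is wrong for that group, not merely incomplete.

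If a site dosed Day 1 from Table 2 and instructed home doses from the bullet, the participant would take 900 mg through Day 8 instead of 1500 mg. The effect on exposure cannot be quantified: the documents give no lenacapavir concentrations for a late start without the Day 2 dose, and they do not say how many participants are still before Week 156.

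The expected frequency is low, because Table 2 is clearly meant to govern and few participants remain. Sample size, power, alpha and the primary endpoint are unaffected. The text should be corrected because a take-home dosing instruction ought to be right for everyone it addresses.

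**What to change.** In the Section 6.3.2 bullet, replace everything from the home-dosing instruction onward, including the weekday clause, with wording to this effect:

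> Remaining doses are taken at home, without regard to food, following the applicable column of Table 2. For a start at 26 to 28 weeks: 300 mg once weekly on the weekday of the first dose. For a start after 28 weeks: 600 mg on Day 2, then 300 mg once weekly from Day 8 on the weekday of the first dose.

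A bare pointer to Table 2 would also remove the contradiction. Writing out both schedules is preferable here because the bullet governs what the participant is told. The wording restates Table 2 and makes no new dosing decision. Footnote a's allowance for on-site dosing is unaffected.

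Make the change in the next amendment, with a short clarification to sites that still have participants to whom the bullet applies. It needs no extra visits or participants. The Day 2 dose uses 2 of the 8 to 10 tablets in the two bottles already allowed, and Section 5.4 permits up to two more bottles.

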6.4. Posttreatment Assessments

6.4.1. Early Termination Visit Assessments

6.4.1.1. Early Termination Visit After Day 1 and Prior to Day 1 SC

If a participant discontinues oral LEN or decides not to initiate SC LEN at Day 1 SC, an early termination visit should be performed within 72 hours of decision to discontinue the study drug. Participants in Cohort 1 will be asked to continue to attend study visits until completion of the Functional Monotherapy Period. Participant will be required to complete the 90-day follow-up visit. Refer to Section 6.4.2.

6.4.1.2. Early Termination Visit After Day 1 SC and Prior to Week 52

If a participant decides to discontinue SC LEN prior to Week 52, an early termination visit should be performed within 72 hours of decision to discontinue study drug.

The participant will be asked to continue attending the scheduled study visits through the Week 52 visit.

- If the participant decides to discontinue SC LEN and agrees to continue to attend study visits through Week 52, no follow-up visits are required.
- If the participant decides to discontinue SC LEN and does not agree to continue to attend study visits through Week 52, the 30-day, 90-day, and 180-day follow-up visits are required. Refer to Section 6.4.2. The 180-day follow-up may be conducted via a phone call per the investigator's discretion.

6.4.1.3. Early Termination Visit After Week 52

If a participant continues the study after completing the Week 52 visit, but discontinues SC LEN prior to study completion, an early termination visit should be performed.

- If the participant discontinues LEN (SC and oral) and continues to attend study visits through their next SC dosing visit, all assessments, except SC dosing, will be performed at the last visit. No further follow-up visits are required.
- If the participant discontinues SC LEN and does not continue to attend study visits through the participant's next SC dosing visit, the 30-day, 90-day, and 180-day follow-up visits are required. Refer to Section 6.4.2. The 180-day follow-up may be conducted via a phone call per the investigator's discretion.
- If a participant discontinues oral LEN during the Oral Bridging Period and does not continue to attend study visits through their next SC dosing visit, the participant will be required to complete the 90-day follow-up visit (see Section 6.4.2).

If there are any abnormal laboratory results with a possible or probable causal relationship with the study drug, every attempt should be made to keep the participant in the study and repeat those laboratory tests weekly (or as often as deemed prudent by the investigator) until the abnormality is resolved, returns to baseline, or is otherwise explained. If this is not possible or acceptable to the participant or investigator, the participant may be withdrawn from the study.

If there are any AEs, every attempt should be made to keep the participant in the study and should be followed up until the AE is resolved or stable. Gilead may request that certain AEs be followed beyond the protocol-defined follow-up period. If this is not possible or acceptable to the participant or investigator, the participant may be withdrawn from the study.

The following evaluations should be performed at the early termination visit:

- Review of AEs and changes in concomitant medications.
- Complete physical examination (urogenital/anorectal examinations will be performed at the discretion of the investigator).
- Vital signs measurement (blood pressure, pulse, respiration rate, and temperature).
- Weight.
- Obtain blood and urine samples as noted in Section 6.5.
- Counsel participant regarding the importance of continuing a complete ART regimen in accordance to standard of care, and refer patient to an appropriate HIV treatment facility.

6.4.1.4. Early Termination Visit After Week 156

If a participant continues the study after completing the Week 156 visit, but discontinues SC LEN prior to study completion, an early termination visit should be performed.

- If the participant discontinues LEN (SC) and continues to attend study visits through their next SC dosing visit, all assessments, except SC dosing, will be performed at the last visit. No further follow-up visits are required.
- If the participant discontinues SC LEN and does not continue to attend study visits through the participant's next SC dosing visit, the 30-day, 90-day, and 180-day follow-up visits are required. Refer to Section 6.4.2. The 180-day follow-up may be conducted via a phone call per the investigator's discretion.

If there are any abnormal laboratory results with a possible or probable causal relationship with the study drug, every attempt should be made to keep the participant in the study and repeat those laboratory tests weekly (or as often as deemed prudent by the investigator) until the abnormality is resolved, returns to baseline, or is otherwise explained. If this is not possible or acceptable to the participant or investigator, the participant may be withdrawn from the study.

If there are any AEs, every attempt should be made to keep the participant in the study and should be followed up until the AE is resolved or stable. Gilead may request that certain AEs be followed beyond the protocol-defined follow-up period. If this is not possible or acceptable to the participant or investigator, the participant may be withdrawn from the study.

The following evaluations should be performed at the early termination visit:

- Review of AEs and changes in concomitant medications.
- Symptom-directed physical examination (urogenital/anorectal examinations will be performed at the discretion of the investigator).
- Vital signs measurement (blood pressure, pulse, respiration rate, and temperature).
- Obtain blood and urine samples as noted in Section 6.5.
- Counsel participant regarding the importance of continuing a complete ART regimen in accordance to standard of care, and refer patient to an appropriate HIV treatment facility.

6.4.2. 30-Day, 90-Day, and 180-Day Follow-Up Visits

The assessments below will be completed for participants who are required to complete 30-day, 90-day, and/or 180-day follow-up visits as noted in Section 6.4.1. Follow-up visits will be scheduled based on the date of the early termination visit. No follow-up visits are required for those participants who do not receive SC LEN at the Week 52 visit.

For scheduling the follow-up visits, a \pm 6-day window may be used.

The following evaluations are to be completed at the follow-up visits:

- Review of AEs and changes in concomitant medications.
- Symptom-directed physical examination.
- Vital signs measurement (blood pressure, pulse, respiration rate, and temperature), including weight.
- Obtain blood and urine samples as noted in Section 6.5.

At the 30-day, 90-day, or 180-day follow-up visit, if there are any abnormal laboratory results indicating that there is a possible or probable causal relationship with the study drug, every attempt should be made to repeat those laboratory tests weekly (or as often as deemed prudent by the investigator) until the abnormality is resolved, returns to baseline, or is otherwise explained. If this is not possible or acceptable to the participant or investigator, the participant may be withdrawn from the study.

If there are any AEs, every attempt should be made to keep the participant in the study and should be followed up until resolution or until the AE is stable, if possible. Gilead may request that certain AEs be followed beyond the protocol-defined follow-up period.

6.5. Clinical Laboratory Assessments

Blood and urine samples will be collected throughout the study as outlined below and in Study Procedures Table ([Appendix 2](#)).

6.5.1. Blood Samples

Blood sample collection for the following laboratory analyses will be performed at every visit, unless specified:

- Serum pregnancy test for all women (screening visit only).
- Serum follicle-stimulating hormone (FSH) test (FSH test is required for women who are < 54 years old and have stopped menstruating for ≥ 12 months but do not have documentation of ovarian hormonal failure) (screening visit only).
- Chemistry profile: alkaline phosphatase, aspartate aminotransferase, ALT, gamma-glutamyl transferase, total bilirubin, direct and indirect bilirubin, total protein, albumin, lactate dehydrogenase, creatine kinase (CK), bicarbonate, blood urea nitrogen, calcium, chloride, creatinine, glucose, lipase, magnesium, phosphorus, potassium, sodium, uric acid (except at the Cohort Selection, Days 2, 5, 16, and 19 visits).
- Estimated GFR (except at the Cohort Selection, Days 2, 5, 16, and 19 visits) according to:
 - Cockcroft-Gault formula for CL_{cr} for participants ≥ 18 years of age.
Men:
$$\frac{(140 - \text{age in years}) \times (\text{wt in kg})}{72 \times (\text{serum creatinine in mg/dL})} = CL_{cr} \text{ (mL/min)}$$

Women:
$$\frac{(140 - \text{age in years}) \times (\text{wt in kg}) \times 0.85}{72 \times (\text{serum creatinine in mg/dL})} = CL_{cr} \text{ (mL/min)}$$
 - Schwartz Formula for participants < 18 years of age.
Adolescent boys ≥ 12 years of age: $0.70 \times L/S_{Cr}$ (L is height in cm).
Adolescent girls ≥ 12 years of age: $0.55 \times L/S_{Cr}$ (L is height in cm).
- Hematology profile: complete blood count with differential and platelet count (except at the Cohort Selection visit, Days 2, 5, 16, and 19 visits).
- CD4+ cell count (except at the Cohort Selection visit, Days 2, 5, 16, and 19 visits).

- Plasma HIV-1 RNA (except at Day 5 and 19).
- HIV-1 genotype and phenotype for protease (PR), RT, integrase (IN), and capsid at screening visit and any subsequent visit with virologic failure (described in Section 6.7).
- HBV serologies (HBV surface antigen, HBV core antibody, HBV surface antibody) (screening only).
- HCV antibody serology (screening only).
- Optional pharmacogenomics testing (Day 1 only, if additional consent for pharmacogenomics testing is obtained and it may be collected at any time during the study).
- Plasma storage samples for optional safety and virology testing (HIV-1 genotype and phenotype) (except at Day 5 and 19).

PK Sampling

PK sampling will occur relative to dosing of LEN at the following time points for all participants:

- Day 1: Predose (within 30 minutes of dosing), 1, 2, 4, 6, and 8 hours postdose.
- Day 2 and 8:
 - Predose (within 30 minutes of dosing).
 - A single timed PK sample between 1 and 6 hours postdose.
- Days 5 (if visit occurs): A single anytime PK sample.
- Day 15 (for Cohort 1B participants only): Predose (within 30 minutes of dosing), 1, 2, 4, 6, and 8 hours postdose.
- Day 16 and 22 (for Cohort 1B participants only):
 - Predose (within 30 minutes of dosing).
 - A single timed PK sample between 1 and 6 hours postdose.
- Days 19 (for Cohort 1B participants only, if visit occurs): A single anytime PK sample.
- During the Maintenance Period, at all visits without SC LEN injections, including the Oral Bridging visits, if applicable: A single anytime PK sample will be collected.

- During the Maintenance Period, at all visits with SC LEN injections, including when SC LEN injection is resumed after the Oral Bridging visits, if applicable: A single predose (within 30 minutes of dosing) PK sample will be collected (while participants are continuing to receive study drug).

At Week 156 and thereafter, upon regulatory and/or IRB/IEC approval of the protocol and when participants have provided written informed consent of the most current IRB-approved consent form, participants will continue to receive study drug every 26 weeks, and continue to attend visits every 26 weeks (± 2 weeks). Participants will not be required to provide PK samples for these visits.

